## **8.2. DATA QUALITY ASSURANCE**

A risk-based approach is used for trial quality management. It is initiated by the assessment of critical data and processes for trial subject protection and reliability of the results as well as identification and assessment of associated risks. An Integrated Quality and Risk Management Plan documents the rationale and strategies for risk management during trial conduct including monitoring approaches, vendor management and other processes focusing on areas of greatest risk.

Continuous risk review and assessment may lead to adjustments in trial conduct, trial design or monitoring approaches.

A quality assurance audit/inspection of this trial may be conducted by the sponsor, sponsor's designees, or by IRB / IEC or by regulatory authorities. The quality assurance auditor will have access to all medical records, the investigator's trial-related files and correspondence, and the informed consent documentation of this clinical trial.

## **8.3. RECORDS**

CRFs for individual subjects will be provided by the sponsor. For drug accountability, refer to Section [4.1.8](#).

### **8.3.1. Source documents**

In accordance with regulatory requirements, the investigator should prepare and maintain adequate and accurate source documents and trial records for each trial subject that include all observations and other data pertinent to the investigation. Source data as well as reported data should follow the 'ALCOA principles' and be attributable, legible, contemporaneous, original, and accurate. Changes to the data should be traceable (audit trail).

Data reported on the CRF must be consistent with the source data or the discrepancies must be explained.

Before providing any copy of subjects' source documents to the sponsor, the investigator must ensure that all subject identifiers (e.g. subject's name, initials, address, phone number, and social security number) have properly been removed or redacted to ensure subject confidentiality.

If the subject is not compliant with the protocol, any corrective action (e.g. re-training) must be documented in the subject file.

For the CRF, data must be derived from source documents, for example:

- Subject identification: sex, year of birth (in accordance with local laws and regulations)
- Subject participation in the trial (substance, trial number, subject number, date subject was informed)
- Dates of subject's visits, including dispensing of trial medication
- Medical history (including trial indication and concomitant diseases, if applicable)
- Medication history
- AEs and outcome events (onset date [mandatory], and end date [if available])
- SAEs (onset date [mandatory], and end date [if available])
- Concomitant therapy (start date, changes)
- Originals or copies of laboratory results and other imaging or testing results, with proper documented medical evaluation (in validated electronic format, if available)
- ECG results (original or copies of printouts)
- Completion of subject's participation in the trial (end date; in case of premature discontinuation, document the reason for it, if known)
- Prior to allocation of a subject to a treatment into a clinical trial, there must be documented evidence in the source data (e.g. medical records) that the trial participant meets all inclusion criteria and does not meet any exclusion criteria. The absence of records (either medical records, verbal documented feedback of the subject or testing conducted specific for a protocol) to support inclusion/exclusion criteria does not make the subject eligible for the clinical trial.

### **8.3.2. Direct access to source data and documents**

The investigator /institution will allow site trial-related monitoring, audits, IRB / IEC review and regulatory inspections. Direct access must be provided to the CRF and all source documents/data, including progress notes, copies of laboratory and medical test results, which must be available at all times for review by the Clinical Research Associate (CRA), auditor and regulatory inspector (e.g. FDA). They may review all CRFs and informed consents. The accuracy of the data will be verified by direct comparison with the source documents described in section [8.3.1](#). The sponsor will also monitor compliance with the protocol and GCP.

### **8.3.3. Storage period of records**

#### **Trial site:**

The trial site(s) must retain the source and essential documents (including ISF) according to contract or the local requirements valid at the time of the end of the trial (whatever is longer).

Sponsor:

The sponsor must retain the essential documents according to the sponsor's SOPs.

#### **8.4. EXPEDITED REPORTING OF ADVERSE EVENTS**

BI is responsible to fulfil their legal and regulatory reporting obligation in accordance with regulatory requirements.

#### **8.5. STATEMENT OF CONFIDENTIALITY AND SUBJECT PRIVACY**

Individual subject data obtained as a result of this trial is considered confidential and disclosure to third parties is prohibited with the exceptions noted in section [8.7](#).

Data protection and data security measures are implemented for the collection, storage and processing of patient data in accordance with the principles 6 and 12 of the WHO GCP handbook.

Personalised treatment data may be given to the subject's personal physician or to other appropriate medical personnel responsible for the subject's welfare. Data generated at the site as a result of the trial need to be available for inspection on request by the participating physicians, the sponsor's representatives, by the IRB / IEC and the regulatory authorities.

##### **8.5.1. Collection, storage and future use of biological samples and corresponding data**

Measures are in place to comply with the applicable rules for the collection, storage and future use of biological samples and clinical data, in particular

- Sample and data usage have to be in accordance with the informed consent
- The BI-internal facilities storing biological samples from clinical trial participants as well as the external storage facility are qualified for the storage of biological samples collected in clinical trials.
- An appropriate sample and data management system, incl. audit trail for clinical data and samples to identify and destroy such samples according to ICF is in place
- A fit for the purpose documentation (biomarker proposal, analysis plan and report) ensures compliant usage
- A fit for purpose approach will be used for assay/equipment validation depending on the intended use of the biomarker data

Samples and/or data may be transferred to third parties and other countries as specified in the ICF.

#### **8.6. TRIAL MILESTONES**

The **start of the trial** is defined as the date when the first subject in the whole trial signs informed consent.

The **end of the trial** is defined as the 'date of the last visit of the last subject in whole trial' ('Last Subject Completed') or 'end date of the last open AE' or 'date of the last follow-up test' or 'date of an AE has been decided as sufficiently followed-up', whichever is latest.

**Early termination of the trial** is defined as the premature termination of the trial for any reason before the end of the trial as specified in this protocol.

**Temporary halt of the trial** is defined as any unplanned interruption of the trial by the sponsor with the intention to resume it.

**Suspension of the trial** is defined as an interruption of the trial based on a Health Authority request.

When the trial is completed, the investigator should inform the head of the trial site in writing of the completion of the trial, and the head of the trial site should promptly inform the IRB and sponsor in writing of the completion.

## 8.7. ADMINISTRATIVE STRUCTURE OF THE TRIAL

The trial is sponsored by Boehringer Ingelheim (BI).

The trial will be conducted at [REDACTED] under the supervision of the Principal Investigator.

Relevant documentation on the participating (Principal) Investigators (e.g. their curricula vitae) will be filed in the ISF.

BI has appointed a CTL, responsible for coordinating all required trial activities, in order to

- Manage the trial in accordance with applicable regulations and internal SOPs
- Direct the clinical trial team in the preparation, conduct, and reporting of the trial
- Ensure appropriate training and information of CTM, CRA and investigators of participating trial sites

The trial medication will be provided by the [REDACTED]  
[REDACTED].

Safety laboratory tests will be performed by the local laboratory of the trial site.

Analyses of BI 1323495 and itraconazole concentrations and biomarker in plasma will be performed at the [REDACTED]  
[REDACTED].

On-site monitoring will be performed by BI or a contract research organisation appointed by BI.

Data management and statistical evaluation will be done by BI or contract research organization according to BI SOPs.

Tasks and functions assigned in order to organise, manage, and evaluate the trial are defined according to BI SOPs. A list of responsible persons and relevant local information can be found in the ISF.

## **10. APPENDICES**

Not applicable.

Proprietary confidential information © 2021 Boehringer Ingelheim International GmbH or one or more of its affiliated companies

## 11. DESCRIPTION OF GLOBAL AMENDMENT(S)

### 11.1. GLOBAL AMENDMENT 1

Date of amendment	23 SEP 2020
BI Trial number	1405-0003
BI Investigational Medicinal Product(s)	BI 1323495
Title of protocol	Safety, tolerability and pharmacokinetics of single rising oral doses of BI 1323495 versus placebo in healthy male Japanese subjects genotyped as poor and extensive metabolizers of UGT2B17 (single-blind, randomised, placebo-controlled [within dose groups] trial), including an investigation of drug-drug interaction with itraconazole in healthy male subjects genotyped as poor metabolizers of UGT2B17 (an open-label, two-period, fixed sequence trial)
To be implemented only after approval of the IRB / IEC / Competent Authorities	
To be implemented immediately in order to eliminate hazard – IRB / IEC / Competent Authority to be notified of change with request for approval	
Can be implemented without IRB / IEC / Competent Authority approval as changes involve logistical or administrative aspects only	
Section to be changed	Section 1.4.2
Description of change	Amended description of risk mitigation action for COVID-19.
Rationale for change	Updated to accept other than PCR testing.
Section to be changed	Section 4.1.2
Description of change	Adding more explanation about rationale of selecting 10 mg for DDI part.
Rationale for change	Based on comment from authority.
Section to be changed	Section 5.6.1

Proprietary confidential information © 2021 Boehringer Ingelheim International GmbH or one or more of its affiliated companies

Description of change	Adding more explanation about handling of genotyping samples and result.
Rationale for change	Based on comment from authority.

## 11.2. GLOBAL AMENDMENT 2

Date of amendment	25 FEB 2020
BI Trial number	1405-0003
BI Investigational Medicinal Product(s)	BI 1323495
Title of protocol	Safety, tolerability and pharmacokinetics of single rising oral doses and multiple oral doses of BI 1323495 versus placebo in healthy male Japanese subjects genotyped as poor and extensive metabolizers of UGT2B17 (single-blind, randomised, placebo-controlled [within dose groups] trial), including an investigation of drug-drug interaction with itraconazole in healthy male subjects genotyped as poor metabolizers of UGT2B17 (an open-label, two-period, fixed sequence trial)
To be implemented only after approval of the IRB / IEC / Competent Authorities	
To be implemented immediately in order to eliminate hazard – IRB / IEC / Competent Authority to be notified of change with request for approval	
Can be implemented without IRB / IEC / Competent Authority approval as changes involve logistical or administrative aspects only	
Section to be changed	Flowchart
Description of change	Minor correction due to typo to SRD part and DDI part. New Flowchart for additional MD part added.
Rationale for change	Same as above
Section to be changed	Section 1.2.1
Description of change	Updated safety and PK information from ongoing studies (1405-0002).
Rationale for change	Updated to latest information.

Proprietary confidential information © 2021 Boehringer Ingelheim International GmbH or one or more of its affiliated companies

Section to be changed	Section 1.3
Description of change	Added rationale for additional MD part
Rationale for change	Same ad above
Section to be changed	Section 2
Description of change	Added endpoints for MD part including PD.  Primary end points is same with SRD part. Secondary endpoints newly added for MD part.  PK related further objectives added for MD part. PD endpoints in MD part added.
Rationale for change	Same as above
Section to be changed	Section 3.1, 3.2 and 3.3
Description of change	Added explanation of additional MD part study design.
Rationale for change	Same as above
Section to be changed	Section 4.1
Description of change	Added dose selection rationale and drug assignment for additional MD part
Rationale for change	Same as above
Section to be changed	Section 4.2
Description of change	Added explanation about restriction for additional MD part.
Rationale for change	Same as above
Section to be changed	Section 5.4.1
Description of change	Added explanation about detailed process of additional PD analysis for additional MD part.
Rationale for change	Same as above
Section to be changed	Section 6.2.2
Description of change	Added explanation about visit schedule of treatment period in additional MD part.
Rationale for change	Same as above
Section to be changed	Section 7
Description of change	Added explanation planned analysis and determination of sample size for additional MD part.

Proprietary confidential information © 2021 Boehringer Ingelheim International GmbH or one or more of its affiliated companies

Rationale for change		Same as above

## **2. LIST OF ABBREVIATIONS**

Term	Definition / description
AE	Adverse Event
AESI	Adverse event of special interest
ALT	Alanine aminotransferase
AST	Aspartate aminotransferase
AUC 0-12	Area under the concentration-time curve of the analyte in plasma over a uniform dosing interval of 12 h after administration of the first dose
AUC 0-∞	Area under the concentration-time curve of the analyte in plasma over the time interval from 0 extrapolated to infinity
AUC 0-tz	Area under the concentration-time curve of the analyte in plasma over the time interval from 0 to the last quantifiable data point
AUC τ,ss	Area under the concentration-time curve of the analyte in plasma at steady state over a uniform dosing interval $\tau$
BI	Boehringer Ingelheim
BP	Blood pressure
C max	Maximum measured concentration of the analyte in plasma
C max,ss	maximum measured concentration of the analyte in plasma at steady state over a uniform dosing interval $\tau$
COVID	Coronavirus disease
CRF	Case Report Form
CTP	Clinical Trial Protocol
CTR	Clinical Trial Report
CV	Arithmetic coefficient of variation
DDI	Drug-drug interaction
ECG	Electrocardiogram
EM	Extensive metabolizer
gCV	geometric coefficient of variation
gMean	Geometric mean
ICH	International Council for Harmonisation of Technical Requirements for Pharmaceuticals for Human Use
IPD	Important protocol deviations
IQRMP	Integrated quality and risk management plan

Term	Definition / description
MD	Multiple doses
MedDRA	Medical Dictionary For Regulatory Activities
NE	Neutrophil Elastase
PD	pharmacodynamic
PK	Pharmacokinetics
PKS	Pharmacokinetic parameter analysis set
PM	Poor metabolizer
PR	Pulse rate
RAGe	Report appendix generator
RPM	Report Planning Meeting
RR interval	ECG interval from the peak of the R wave to the peak of the subsequent R wave
SAE	Serious adverse event
SD	Standard Deviation
SOC	System Organ Class
SRD	Single rising dose
TS	Treated set
TSAP	Trial Statistical Analysis Plan
ULN	Upper limit of normal range

### **3. INTRODUCTION**

As per ICH E9 ([1](#)), the purpose of this document is to provide a more technical and detailed elaboration of the principal features of the analysis described in the protocol, and to include detailed procedures for executing the statistical analysis of the primary and secondary variables and other data.

This TSAP assumes familiarity with the Clinical Trial Protocol (CTP), including Protocol Amendments. In particular, the TSAP is based on the planned analysis specification as written in CTP Section 7 “Statistical Methods and Determination of Sample Size”. Therefore, TSAP readers may consult the CTP for more background information on the study, e.g., on study objectives, study design and population, treatments, definition of measurements and variables, planning of sample size, randomization.

Study data will be stored in a trial database within Medidata Rave system.

The statistical analyses will be performed within the validated working environment CARE, including SASTM (Version 9.4 or higher, by [REDACTED]), and a number of SASTM-based tools (e.g., macros for the analyses of AE data or laboratory data; Report Appendix Generator system (RAGe) for compilation/formatting of the CTR appendices).

PK parameters will be calculated using Phoenix WinNonlinTM software (version Phoenix 6.3 or higher, [REDACTED]).

#### **4. CHANGES IN THE PLANNED ANALYSIS OF THE STUDY**

All analyses described in this TSAP are in accordance with the statistical methods described in the revised CTP.

## **5. ENDPOINTS**

### **5.1 PRIMARY ENDPOINTS**

#### **Section 2.1.2 of the CTP:**

*SRD and MD part; The primary endpoint for assessment of safety and tolerability of BI 1323495 is the percentage of subjects with drug-related adverse events.*

*DDI part; The following pharmacokinetic parameters will be determined for BI 1323495:*

- $AUC_{0-\infty}$  (area under the concentration-time curve of the analyte in plasma over the time interval from 0 extrapolated to infinity)
- $C_{max}$  (maximum measured concentration of the analyte in plasma)

### **5.2 SECONDARY ENDPOINTS**

#### **5.2.1 Key secondary endpoints**

This section is not applicable as no key secondary endpoints have been defined in the CTP.

#### **5.2.2 Secondary endpoints**

#### **Section 2.1.3 of the CTP:**

*SRD part; The following pharmacokinetic parameters will be determined if feasible:*

- $AUC_{0-\infty}$  (area under the concentration-time curve of the analyte in plasma over the time interval from 0 extrapolated to infinity)
- $C_{max}$  (maximum measured concentration of the analyte in plasma)

*DDI part; The following pharmacokinetic parameters will be determined for BI 1323495 if feasible:*

- $AUC_{0-tz}$  (area under the concentration-time curve of the analyte in plasma over the time interval from 0 to the last quantifiable data point)

*MD part; The following pharmacokinetic parameters will be determined if feasible:*

[figure not shown]
*After the first dose of BI 1323495:*

[figure not shown]
- $AUC_{0-12}$  (area under the concentration-time curve of the analyte in plasma over a uniform dosing interval of 12 h after administration of the first dose)
- $C_{max}$  (maximum measured concentration of the analyte in plasma after the first dose)

*After the last dose of BI 1323495:*

- $AUC_{\tau,ss}$  (area under the concentration-time curve of the analyte in plasma at steady state over a uniform dosing interval  $\tau$ )

- $C_{max,ss}$  (maximum measured concentration of the analyte in plasma at steady state over a uniform dosing interval  $\tau$ )

## **6. GENERAL ANALYSIS DEFINITIONS**

### **6.1 TREATMENTS**

For basic study information on treatments to be administered, assignment of treatment groups, and selection of doses, cf. Section 4 of the CTP.

**SRD part, PM:** 24 subjects were planned to be treated with

- doses of 10 mg (1 x 10 mg tablet), 30 mg (3 x 10 mg tablets), or 100 mg (2 x 50 mg tablets) of BI 1323495 on Day 1 (test treatment)
- or matching placebo (reference treatment).

**SRD part, EM:** 12 subjects were planned to be treated with

- doses of 30 mg (3 x 10 mg tablets), 70 mg (2 x 10 mg tablets and 1 x 50 mg tablet) or 150 mg (3 x 50 mg tablets) of BI 1323495 on Day 1 (test treatments)
- or matching placebo (reference treatment).

**MD part, PM:** 24 subjects were planned to be treated with

- doses of 30 mg (3 x 10 mg tablets twice daily for 10 days and single dose on Day 11) or 60 mg (1 x 10 mg tablet and 1 x 50 mg tablet once daily for 11 days) of BI 1323495 (test treatment)
- or matching placebo (reference treatment).

**DDI part, PM:** Subjects were planned to be treated with

- a dose of 10 mg (1 tablet as single dose on Day 1 of period 1) of BI 1323495 (reference treatment)
- and – after a washout period of at least 11 days – doses of 10 mg (1 tablet as single dose on Day 1) of BI 1323495 and 200 mg of itraconazole once daily on Days -3 to 7 (test treatment).

In the SRD and MD parts, subjects are planned to be randomised within each dose group in a 3:1 ratio (test treatment to placebo). In the DDI part, randomisation is not applicable, because all subjects are planned to receive the same treatment in the same order.

The following study phases will be defined for the analysis of AEs:

Table 6.1: 1 Analysis phases and labels for statistical analyses in the SRD and MD parts

Study analysis phase	Label	Start	End
Screening 	Screening	Date of informed consent	Date/time of first administration of BI 1323495 or placebo
On treatment	Placebo SRD PM 10 mg, SRD PM 30 mg, SRD PM 100 mg, SRD EM 30 mg, SRD EM 70 mg, SRD EM 150 mg, MD PM 30 mg BID, MD PM 60 mg QD, respectively	Date/time of first administration of BI 1323495 or placebo	Date/time of last administration of BI 1323495 or placebo + REP (7 days, i.e., 7 * 24 h)  or  12:00 a.m. on day after last contact date  (whichever occurs first)
Follow-up	Placebo F/U SRD PM 10 mg, F/U SRD PM 30 mg, F/U SRD PM 100 mg, F/U SRD EM 30 mg, F/U SRD EM 70 mg, F/U SRD EM 150 mg, F/U MD PM 30 mg BID, F/U MD PM 60 mg QD, respectively	Date/time of last administration of BI 1323495 or placebo + REP (7 days, i.e., 7 * 24 h)	12:00 a.m. on day after last contact date

 See [Section 6.7](#) for definition of baseline, which will be used in the statistical analyses of safety laboratory data, ECG and vital signs.

For the DDI part of this trial, the following separate phases will be defined for the analyses of AEs:

Table 6.1: 2 Analysis phases and labels for statistical analyses in DDI part

Study analysis phase	Label	Start	End
Screening 	Screening	Date of informed consent	Date/time of first administration of study drug
On treatment: BI Treatment	DDI BI	Date/time of first administration of BI 1323495 or placebo	Date/time of first administration of BI 1323495 + REP (7 days, i.e., 7 * 24 h)
On treatment: Itraconazole (ITZ)	DDI ITZ	Date/time of first administration of itraconazole	Date/time of BI 1323495 administration in treatment period 2 or alternatively, 0:00h on the day after trial termination date in case of no further treatment
On treatment- BI+ ITZ	DDI BI+ITZ	Date/time of BI 1323495 administration in treatment period 2	Date/time of last administration of itraconazole + REP (9 days, i.e., 9 * 24 h) or 12:00 a.m. on day after last contact date (whichever occurs first)
Follow-up BI	F/U DDI BI	End of DDI BI treatment phase (i.e. Date/time of first administration of BI 1323495 + REP (7 days, i.e., 7 * 24 h))	First drug administration of itraconazole or alternatively, 0:00h on the day after trial termination date in case of no further treatment
Follow-up BI	F/U DDI BI+ITZ	End of DDI BI+ITZ treatment phase (i.e. Date/time of last administration of itraconazole + REP (9 days, i.e., 9 * 24 h))	until 0:00h on the day after trial termination date

 See [Section 6.7](#) for definition of baseline, which will be used in the statistical analyses of safety laboratory data, ECG and vital signs.

Two types of AE displays will be provided in the report:

A. Section 15.3 and Appendix 16.1.13.1.8 (only for ClinicalTrials.gov and EudraCT) of the CTR displays:

In these displays, the on treatment phase will be analysed (labelled with the name of the study treatment (short label)). Screening and follow-up periods will not be included in this analysis. The following totals will be provided in addition (Section 15.3 only):

- a total over all on treatment phases involving BI (“**Total BI**”)

- a total over all on treatment phases included in this analysis (“**Total on-trt**”)

**B.** Section 15.4 and Appendix 16.1.13.1.8 (except for ClinicalTrials.gov and EudraCT) of the CTR displays:

- Screening
- On treatment (labelled with the name of the study treatment (short label))
- Follow-up (labelled with the name of the study treatment (short label))

In Section 16.1.13.1.8 AE tables, the following totals will be provided in addition:

- a total over all on treatment phases involving BI (“**Total BI**”)
- a total over all study phases (“**Total**”)

Tables of vital signs and laboratory values will present results by dose group and study period.

For detailed information on the handling of the treatments refer to Technical TSAP ADS plan and Analysis Data Reviewers guide.

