Period 2/Treatment T (BI 1323495 + itraconazole) 	3	-3	-72:00	09:00	Ambulatory visit, itraconazole administration	x B,2,3			x			x 
		-2	-48:00	09:00	Ambulatory visit, itraconazole administration							x 
		-1	-24:00	09:00	Ambulatory visit, itraconazole administration 	x C,2,3		x 				x 
			-12:00	21:00	Admission to trial site 							
	1 		-2:00	07:00			x 		x 	x 	x 	x 
			-1:00	08:00	Itraconazole administration			x 				
			0:00	09:00	BI 1323495 administration							
			0:20	09:20			x					
			0:40	09:40			x					
			1:00	10:00			x					
			1:30	10:30			x					
			2:00	11:00	240 mL fluid intake		x					
			3:00	12:00			x					
			4:00	13:00	240 mL fluid intake, thereafter lunch 		x		x	x	x	
			5:00	14:00			x					
			6:00	15:00			x					
			7:00	16:00	Snack (voluntary) 		x					
			8:00	17:00			x					
			9:00	18:00			x					
			10:00	19:00	Dinner 		x					
			12:00	21:00			x					x
	2		23:00	08:00	Itraconazole administration	x B,2						x
			24:00	09:00	Breakfast (voluntary) 		x		x	x	x	
			28:00	13:00	Lunch (voluntary)							
			31:00	16:00	Snack (voluntary)							x
			34:00	19:00	Discharge from trial site		x					x
	3		47:00	08:00	Ambulatory visit, itraconazole administration		x 	x 				x
			71:00	08:00	Ambulatory visit, itraconazole administration	x C,2	x 					x
	4		95:00	08:00	Ambulatory visit, itraconazole administration		x 					x
			119:00	08:00	Ambulatory visit, itraconazole administration	x C,2	x 					x
			143:00	08:00	Ambulatory visit, itraconazole administration		x 	x 				x
			167:00	08:00	Ambulatory visit	x B	x	x				x
EOT	4	16 to 23			End of trial (EOT) examination 	x A			x	x	x	x

Clock time should be adjusted based on actual administration time

1. Subject must be informed and written informed consent obtained prior to starting any screening procedures. Screening procedures include medical examination, check of vital signs, ECG(12-lead ECG), chest x-ray, safety laboratory (including drug screening), pharmacogenetic analysis for UGT2B17 genotype, demographics (including determination

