**Table 4.1.4: 3 Dosage and treatment schedule in the DDI part**

Treatment period	Treatment	Substance	Formulation	Unit strength	Dosage	Total dose
1	R (Reference)	BI 1323495	Tablet, film-coated	10 mg	1 tablet as single dose (Day 1)	10 mg
2	T (Test)	BI 1323495	Tablet, film-coated	10 mg	1 tablet as single dose (Day 1)	10 mg
		Itraconazole	Oral solution	10 mg/mL	20 mL (200 mg) qd for 10 days (Days -3 to 7)	2000 mg

Table 4.1.4: 4 BI 1323495 and placebo treatments, tablets of MD part for PM

Dose group	Substance	Pharmaceutical form	Unit strength	Number of units per administration	Total daily dose of BI 1323495
1	BI 1323495	Tablet, film-coated	10 mg	3 tablets bid*	60 mg
1	Placebo	Tablet, film-coated	--	3 tablets bid*	--
2	BI 1323495	Tablet, film-coated	10 mg 50 mg	1 tablet each qd	60 mg
2	Placebo	Tablet, film-coated	--	1 tablet each qd	60 mg

\*On Day 11, Subjects will receive a single dose in the morning only. On all other trial days, BI 1323495 will be administered bid.

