#### **7.3.4. Safety analyses**

Safety will be assessed as defined by the endpoints listed in Section [2.1.2](#) and [2.2.2.1](#) based on the treated set (TS). Safety analyses will be descriptive in nature and will be based on BI standards.

For all analyses the treatment actually administered (= treatment at onset) to the subject will be used (any deviations from the randomised treatment will be discussed in the minutes of the Report Planning Meeting).

Treatments will be compared in a descriptive way. In SRD part, the placebo group in the safety evaluation will consist of all subjects treated with placebo, regardless of the dose group in which they were treated. The test treatment groups will be compared to the placebo group in a descriptive way. In DDI part, the test treatment groups (BI 1323495+itraconazole) will be compared to the reference group (BI 1323495 alone) in a descriptive way. Tabulations of frequencies/proportions will be used for the evaluation of categorical (qualitative) data, and tabulations of descriptive statistics will be used to analyse continuous (quantitative) data.

Measurements (such as ECGs, vital signs, or laboratory parameters) or AEs will be assigned to treatments (see Section [4.1](#)) based on the actual treatment at the planned time of the measurement or on the recorded time of AE onset (concept of treatment-emergent AEs). Therefore, measurements planned or AEs recorded prior to intake of trial medication will be assigned to the screening period, those between the first trial medication intake and end of REP (see Section [1.2.3](#)) will be assigned to the treatment period. Events occurring after the REP but prior to next intake or end of trial termination date will be assigned to 'follow-up'. These assignments including the corresponding time intervals will be defined in detail in the TSAP. Note that AEs occurring after the last per protocol contact but entered before database lock will be reported to Pharmacovigilance only and will not be captured in the trial database.

Additionally, further treatment intervals (called analysing treatments) may be defined in the TSAP in order to provide summary statistics for other than above periods, such as combined treatments, on-treatment totals, or periods without treatment effects (such as screening and post-trial intervals).

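### The DDI safety comparison counts subjects with AEs over about 359 h with itraconazole but 168 h for BI 1323495 alone, with no stated allowance for window length

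*SAP*

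**What the plan says.** SAP 6.1, Table 6.1: 2 defines the DDI phases used to assign AEs:

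- **R (DDI BI)** starts at "Date/time of first administration of BI 1323495 or placebo" and ends at "Date/time of first administration of BI 1323495 + REP (7 days, i.e., 7 * 24 h".
- **T (DDI BI+ITZ)** starts at "Date/time of BI 1323495 administration in treatment period 2" and ends at "Date/time of last administration of itraconazole + REP (9 days, i.e., 9 * 24 h", or at "12:00 a.m. on day after last contact date (whichever occurs first".
- The three days of itraconazole alone before the second BI 1323495 dose form a separate phase. So does the follow-up after R.

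The residual effect periods come from protocol 1.2.3: about 7 days for BI 1323495, and 9 days after the Day 7 itraconazole dose for Treatment T.

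Protocol 7.3.4 states that "the test treatment groups (BI 1323495+itraconazole) will be compared to the reference group (BI 1323495 alone) in a descriptive way". SAP 7.8.1 bases all AE analyses on the number of subjects with AEs, not on the number of AEs. SAP 6.1 leaves screening and follow-up phases out of the Section 15.3 displays and shows them as separate columns in the Section 15.4 displays. The visible text gives no exposure-adjusted rate, common window or caveat on phase length for the DDI part.

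**The concern.** The chance that a subject has at least one AE grows with the time over which AEs are counted. If one column covers about twice the time of the other, the crude percentages mix treatment with window length, and the percentages alone cannot separate them. An event on Day 9 after the R dose leaves the R column; an event on Day 9 after the T dose stays in the T column.

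What is at stake is how the stated safety comparison reads in the report: an apparent excess of AEs with itraconazole could be partly or wholly a product of the longer window. The DDI primary endpoints, AUC0-∞ and Cmax, do not depend on these phases.

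**Working it through.** **1. Last itraconazole dose.** Protocol Table 4.1.4: 3 gives "20 mL (200 mg) qd for 10 days (Days -3 to 7". With no Day 0, Days -3 to -1 and 1 to 7 make 3 + 7 = 10 doses, and 10 × 200 mg = 2000 mg, the total in that table. The protocol Flow Chart puts the last row marked "Ambulatory visit, itraconazole administration" at 143:00 h, 08:00. Check: Day 1 09:00 to Day 7 08:00 is 6 × 24 − 1 = 143 h.

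**2. Window lengths.**

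- R: 7 × 24 = 168 h.
- T: 143 + 9 × 24 = 143 + 216 = 359 h, or 14.96 days, ending on Day 16 at 08:00.
- Ratio: 359 / 168 = 2.14. Difference: 359 − 168 = 191 h.

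**3. Does the last-contact limit shorten T?** The end-of-trial visit is on Day 16 to 23. For a completer the earliest limit is 00:00 on Day 17, which is 16 × 24 − 9 = 375 h after the dose. That is later than 359 h, so the limit does not bind. It can bind for subjects who leave early.

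**4. Could R be extended to match T?** Not reliably. At the minimum washout of 11 days, itraconazole starts 11 × 24 − 72 = 192 h after the R dose. The R follow-up column may therefore cover only 192 − 168 = 24 h.

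**5. Illustration with no treatment effect.** The documents give no background AE rate per day, so the R proportion p is an assumption. With a constant hazard of recorded AEs, the T proportion is 1 − (1 − p)^(359/168):

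| R | 5% | 10% | 20% | 25% | 30% | 40% |
|---|---|---|---|---|---|---|
| T | 10.4% | 20.2% | 37.9% | 45.9% | 53.3% | 66.4% |

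The 25% column corresponds to 3 of 12 subjects with AEs in the fasted period of the food-effect trial (protocol 1.2.1); the length of that AE window is not stated. With 14 subjects, 25% means 14 × 0.25 = 3.5 expected in R and 14 × 0.459 = 6.4 in T. Treating the periods as independent binomials, the probability that T exceeds R is 0.84 and that R exceeds T is 0.08. With equal windows each is 0.41. Over the 5 to 40% range, the probability that T exceeds R is 0.56 to 0.89, against 0.31 to 0.42 with equal windows.

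**6. Sensitivity to late recording.** Suppose that AEs are recorded after 168 h at a fraction f of the earlier rate. The exponent is then 1 + f × 191/168. At f = 1 the table above applies. At f = 0.5 (assumption) the exponent is 1.568, and 10/20/30% in R becomes 15.2/29.5/42.8% in T. At f = 0 there is no difference.

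**The case against.** The strongest reply is that the unequal windows are deliberate. Protocol 1.2.3 expects that itraconazole may raise and prolong exposure to BI 1323495, so a longer T phase is right for capturing safety events. This stands. A reader might infer that the phase definitions are wrong and should be replaced, but the documents do not support that. The weakness is confined to comparing crude percentages from phases of different length.

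A reader might also infer that T will look worse than R. That goes too far: the tendency is in expectation, and with 14 subjects the observed T percentage need not exceed R. Nor does a longer window add repeat events to the percentage, because the SAP counts subjects.

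The constant-hazard figures are open to challenge, and this also stands. AE questioning runs to 167 h in both periods, but in Period 2 none is scheduled between 167 h and the end-of-trial visit. Most of the extra 191 h therefore depends on spontaneous report or later recall. Dosing, confinement and most blood sampling fall early. For drug-related AEs the effect is likely smaller still, since background events judged unrelated do not enter that measure.

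Individual listings and the separate follow-up column help a careful reader, but only in part: follow-up is absent from Section 15.3 and may last only 24 h after R. AE presentation also defers to a sponsor standard not available here, so the lack of an adjustment is established only for the visible text.

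Finally, a 168 h window ends 168 − 143 = 25 h after the last itraconazole dose, whose half-life is about 40 h (protocol 1.2.2). Used alone, it would hide late T events that protocol 1.2.3 anticipates. That argues for adding the matched comparison, not substituting it.

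**Conclusion.** The point holds as a modest one. For completers at planned times, the T window is 359 h and the R window 168 h, a ratio of 2.14, and the planned descriptive comparison makes no visible allowance for it. If any background AEs occur and are recorded after 168 h, the T percentage is biased upwards relative to R in expectation.

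The 2.14 is a ratio of window lengths, not an estimate of inflation in the AE percentage. The size of the bias is unknown. The constant-hazard values in step 5 rest on an assumed background rate and full recording after 168 h, and serve as an upper illustration.

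DDI safety is a further objective assessed descriptively, with no hypothesis test and no stated decision rule based on T versus R percentages. PK conclusions are unaffected. This is a cheap improvement to a stated comparison, not a flaw in the trial's main inference.

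**What to change.** - Keep the REP-based phases, listings and tables as planned for safety capture.
- Add one supplementary T versus R table, for all AEs and for drug-related AEs, limited to AEs with onset 0 to 168 h after the BI 1323495 dose in each period. This window fits R even at the minimum washout (192 h), and scheduled AE questioning runs to 167 h in both periods.
- Print phase length or subject-days for each DDI column of the REP-based table.

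Protocol 7.3.4 already lets the TSAP define further treatment intervals for summaries, so a short addition to the SAP should be enough.

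The cost is one extra table and a sentence. T events after 168 h do not appear in the new table but remain in the REP-based one. The matched window removes only the difference in length; it does not separate AEs due to itraconazole itself or effects of the fixed sequence, and the table should say so.
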